**ATTACHMENT 2: PHARMACOKINETIC AND BIOMARKER SAMPLING SCHEDULE**

Detailed instructions on sample collection and shipment can be found in the Laboratory Manual.

Study Day	Time point (Relative to CB-839 Dosing)	Phase 1 only PK/ Biomarker	Phase 2 only PK/ Biomarker	Phase 1 and Phase 2 Biomarker: RNA	Phase 1 and Phase 2 Biomarker: CPT	Phase 1 and Phase 2 Biomarker: TCR^6	Phase 1 and Phase 2 Tumor Biopsy
Screening							4-6 Cores
Cycle 1 Day 1	Predose	3 mL	3 mL	5 mL	32 mL	3 mL	
Cycle 1 Day 1	0.5 hr	3 mL					
Cycle 1 Day 1	1 hr	3 mL					
Cycle 1 Day 1	2 hr	3 mL					
Cycle 1 Day 1	4 hr	3 mL					
Cycle 1 Day 1	6 hr	3 mL					
Cycle 1 Day 1	8 hr	3 mL					
Cycle 1 Day 15	Predose	3 mL	3 mL	5 mL		3 mL	
Cycle 1 Day 15	0.5 hr	3 mL					
Cycle 1 Day 15	1 hr	3 mL					
Cycle 1 Day 15	2 hr	3 mL					
Cycle 1 Day 15	4 hr	3 mL					
Cycle 1 Day 15	6 hr	3 mL					
Cycle 1 Day 15	8 hr	3 mL					
Cycle 2 Day 1	Predose	3 mL	3 mL	5 mL	32 mL		4-6 Cores
Cycle 3 Day 1	Predose	3 mL	3 mL	5 mL	32 mL	3 mL	
Total sample collected		48 mL blood	12 mL blood	20 mL blood	96 mL blood	9 mL blood	

1. Where applicable, the collection window is  $\pm 15$  minutes. The actual sample collection time will be entered in the EDC.
2. Blood samples will be collected for all patients enrolled in the Phase 1 Dose Escalation.
3. Blood samples will be collected from all patients enrolled in the Phase 2 Dose Expansion
4. 2.5 mL of whole blood will be collected in to two Paxgene Blood RNA tubes.

5. 8 mL of whole blood will be collected in to four Vacutainer CPT cell preparation tubes with sodium heparin. The CPT tubes will be centrifuged at room temperature for 30 min at 1800 RCF (relative centrifugal force).
6. 3mL of whole blood will be collected in to 1 EDTA tubes. The EDTA tubes should be placed in -80°C storage.
7. At least 4-6 tissue cores will be collected from patients. 14-18 gauge needle core biopsies are preferred however, 20 gauge needles can be used at the discretion of the radiologist and treating physician. For melanoma patients, excisional or punch biopsies are preferred.

**ATTACHMENT 3: CLINICAL LABORATORY TESTS****Hematology (Peripheral Blood Sample)**

- Hemoglobin and hematocrit
- RBC count
- White blood cell count with differential
- Platelet count

**Coagulation Tests**

- PT, aPTT and INR

**Serum Chemistry-Full Metabolic Panel (Peripheral Blood Sample) with additional analytes**

- |                        |  |
|------------------------|--|
| • Sodium               | • Total protein                                  |
| • Potassium            | • Albumin  |
| • Chloride             | • Total bilirubin                    |
| • CO 2      | • Aspartate aminotransferase (AST)               |
| • Calcium              | • Alanine aminotransferase (ALT)                 |
| • Glucose  | • Alkaline phosphatase (AP)                      |
| • Blood urea nitrogen  | • Lactate dehydrogenase (LDH)                    |
|                        | • Creatinine                                     |
|                        | • Thyroid Stimulating Hormone (TSH)  |

 Fasting glucose (8-10 hour fast) is required on PK days only (C1D1, C1D15, C2D1 and C3D1).

 Thyroid functioning will be monitored by measuring thyroid stimulating hormone (TSH) only, with a full panel run of TFTs if there is an abnormal TSH result or thyroid dysfunction is suspected.

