  - b. It was performed at least 4 weeks after the date of a prior scan demonstrating progressive disease on anti-PD-1/PD-L1 containing therapy in the immediate prior line of therapy
- Cohort 4 patients must have screening contrast-enhanced MRI of the brain to assess for brain metastases within 28 days before C1D1

A patient who meets all of the inclusion criteria will enter the study. Screen failures must be captured in the electronic data capture (EDC) system.

## 10.2 Cycle 1

Screening urinalysis, serum chemistry, coagulation, and hematology that occurred *within 3 days* prior to C1D1 do not need to be repeated unless a clinically significant change in the interim is suspected.

Patients should be instructed not to eat breakfast prior to their clinic visit on C1D1 and C1D15. On these days, patients will have all predose procedures performed, take their dose of CB-839 with food then receive nivolumab. Note that all predose assessments must be performed prior to nivolumab and CB-839 administration. The 2nd dose of CB-839 will be self-administered by the patient per dosing instructions after all study procedures have been completed.

A detailed breakdown of the visit schedule and sample collection time points can be found in Attachments 1 and 2. During Cycle 1, patients will undergo the following procedures:

- AE Monitoring
- Recording of concomitant medications
- Vital signs and weight
- Symptom-directed physical exam
- ECOG Performance status evaluation
- Clinical laboratory evaluation (hematology, coagulation, serum chemistry, and urinalysis)
- Plasma sample collection for PK and biomarker analysis
- Whole blood sample collection for biomarker analysis
- ECG with QTcF between 2-4 hr post-dose
- Administration of CB-839 and nivolumab

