## 10.3 Cycle 2 and all subsequent cycles

Patients will return to the clinic and undergo the following procedures:

- AE monitoring
- Recording of concomitant medications

- Vital signs and weight
- Symptom-directed physical exam
- Clinical laboratory values (hematology, coagulation, serum chemistry and urinalysis)
- ECOG performance status evaluation
- Plasma sample for collection for biomarker analysis taken prior to dosing on Cycles 2 and 3 Day 1
- Whole blood sample collection for biomarker analysis taken prior to dosing on Cycles 2 and 3 Day 1
- Administration of CB-839 and nivolumab
  - Patients should be instructed not to eat breakfast prior to their clinic visit on Cycle 2 Day 1 and Cycle 3 Day 1. Patients will undergo the predose assessments prior to receiving the nivolumab infusion or eating breakfast and receiving the CB-839 dose. The 2nd dose of CB-839 will be self-administered by the patient per dosing instructions after all study procedures have been completed.
- A postdose tumor biopsy will be obtained from all patients in Phase 1 backfill cohorts, Phase 2- Cohorts 2, 4, and 5 on Cycle 2 Day 1 only ( $\pm$  1 week). Coagulation tests must be performed and evaluated within 72 to 24 hr prior to all biopsy procedures.
- Radiographic evaluation (e.g., diagnostic CT or MRI) of tumor burden will occur approximately every 8 weeks. The same method of evaluation should be used throughout the course of the study. The scans and redacted reports will be collected and sent to a central reader for exploratory evaluation.

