## 11.0 TEST ARTICLE/STUDY DRUG

### 11.1 Test Article Administration

#### CB-839

Test article (CB-839) will be administered orally using a capsule (200 mg per capsule) or tablet (200 mg per tablet) formulation. CB-839 will be administered only to patients who have signed and dated an Informed Consent Form. CB-839 will be administered on Days 1 through 28 of each 28-day cycle and should be taken orally using the number of capsules or tablets directed in the Pharmacy Manual. CB-839 dosing will not be adjusted for body weight or surface area.

The first CB-839 dose of the day will be administered immediately after breakfast. The evening/second dose should be taken with a meal approximately 12 hr ( $\pm$  2 hr) after the morning dose.

On PK days (Cycle 1 Days 1 and 15, Cycle 2 Day 1 and Cycle 3 Day 1) patients should be instructed NOT to take their morning dose of CB-839 at home. On PK days, patients will have all predose procedures performed, take their dose of CB-839 with food then receive nivolumab. The time of dosing will be recorded in the clinic. The evening dose will be self-administered by the patient after all postdose activities have been completed. On non-PK collection days, patients will administer CB-839 per their usual administration schedule.

Patients who vomit their CB-839 dose should be instructed NOT to make up that dose and to report the frequency of vomiting occurrences associated with study drug administration to the site. Patients who report  $\geq$  3 incidences of vomiting associated with study drug administration will have a blood sample drawn for an unscheduled PK analysis.

Nivolumab: Nivolumab will be administered at a flat dose of 240 mg IV infusion over 60 min on Days 1 and 15 of each 28-day cycle. Nivolumab (Opdivo®) is supplied by Calithera as a

10 mg/mL solution for infusion following dilution. Please refer to the [nivolumab package insert](#) for specific instructions on nivolumab administration.

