**ATTACHMENT 1: SCHEDULE OF STUDY ASSESSMENTS**

Visit	Screening	Cycle 1			Cycle 2+	End of Treatment/ Follow up
	Day -28 to -1	Day 1 (-1 day)	Days 8 and 22 (± 2 days)	Day 15 (± 2 days)	Days 1 and 15 (± 5 days)	EOT: Within 28 days post treatment discontinuation
Written Informed Consent	X					
Inclusion/Exclusion Criteria	X					
Demographics and Medical History	X					
Physical Examination 	X	X	X	X	X 	X
Height	X					
Weight	X	X	X	X	X 	X
Vital Signs 	X	X	X	X	X	X
ECOG Performance Status	X	X			X 	X
12-lead ECG with QTcF 	X	X 		X 		X
Urinalysis 	X	X 	X	X	X	X
Serum Chemistry levels 	X	X 	X	X	X	X
Coagulation tests 	X	X 	X	X	X	X
Hematology 	X	X 	X	X	X	X
Serum or Urine Pregnancy Test 	X					X
Pharmacokinetic (PK) Assay 		X		X	X 	
Biomarker Assay 		X		X	X 	
Nivolumab Dosing 		X		X	X	
CB-839 Dosing 		X	X	X	X	
Baseline Radiographic Evaluation of Tumor Burden (diagnostic CT or MRI)	X 				X 	X 
MRI brain with contrast	X 				X 	
Archival Tumor Collection 	X					
Tumor Biopsy for Tumor Biomarkers 	X				X	
Adverse Events		X	X	X	X	X
Concomitant Medications	X	X	X	X	X	X
Follow up						X 

Explanation of Superscripts

1. Complete physical exam is required at Screening and at End of Treatment. A symptom-directed physical exam can be done on all other visits. System exams are only required as clinically indicated.
2. Assessment to be completed on Day 1 of every cycle.
3. Vital sign measurements include temperature, pulse, respiratory rate and resting systolic and diastolic blood pressure. On the day of nivolumab infusion, vital signs will be obtained pre-infusion and within 30 minutes of the end of the infusion. Vital signs should be collected  $\pm$  5 minutes from the scheduled times noted above.
4. Duplicate ECGs are NOT required.
5. ECG to be performed within approximately 2 to 4 hr postdose of CB-839 administration.
6. Does not need to be repeated if the Screening sample was obtained within 3 days prior to C1D1 unless a clinically significant change is suspected.

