**ATTACHMENT 4: RECIST CRITERIA VERSION 1.1**

Source: [Eisenhauer 2009](#)

Sponsor's Note: CB-839, may affect glucose metabolism in both normal and tumor tissues. Preclinical data suggest that glucose uptake may increase with glutaminase inhibition in sensitive tissues, reflecting the pharmacodynamics effects of CB-839. False positive interpretations of progressive disease with FDG-PET scans may occur. Therefore, all FDG-PET findings suggestive of progressive disease should be confirmed by dedicated anatomic imaging (CT or MRI) for this study.

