### **7.5.3 Laboratory Data**

Laboratory variables will be examined using mean change in value from baseline to scheduled time points. The baseline value of a variable is defined as the last value obtained on or before the date and time of the first dose of CB-839 or nivolumab. Proportion of patients with laboratory measurement outside the normal range and by NCI CTCAE v4.03 grade will be summarized.

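### Fasting glucose is required at only four early visits and baseline may be unfasted, yet the change, range and grade summaries ignore fasting, so glucose change is confounded with meals

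*Protocol*

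**What the plan says.** **Fasting rule.** Protocol Attachment 3, footnote 1 to the serum chemistry panel: "Fasting glucose (8-10 hour fast) is required on PK days only (C1D1, C1D15, C2D1 and C3D1"). The visit instructions match. Section 10.2 has "Patients should be instructed not to eat breakfast prior to their clinic visit on C1D1 and C1D15", and Section 10.3 has "Patients should be instructed not to eat breakfast prior to their clinic visit on Cycle 2 Day 1 and Cycle 3 Day 1".

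**Chemistry schedule.** Attachment 1 schedules chemistry at Screening, C1D1, C1D8, C1D15, C1D22, Days 1 and 15 of every cycle from Cycle 2, and end of treatment. No fasting rule is given for any visit outside the four PK visits. Section 11.1 has the morning dose follow breakfast and adds: "On non-PK collection days, patients will administer CB-839 per their usual administration schedule". Attachment 1 footnote 7 lets the laboratory draw precede dosing by up to 48 hours.

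**Baseline.** Attachment 1 footnote 6 says of the C1D1 sample: "Does not need to be repeated if the Screening sample was obtained within 3 days prior to C1D1" (unless a clinically significant change is suspected). Section 10.2 repeats this. Nothing requires the Screening sample to be fasted. Protocol 16.6 and SAP 7.5.3 take baseline as the last value up to the first dose.

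**Analysis.** SAP 7.5.3, like protocol 16.6: "Laboratory variables will be examined using mean change in value from baseline to scheduled time points". The SAP adds the proportion of patients outside the normal range and by CTCAE grade. Neither document mentions recording fasting status or using it in the analysis.

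**The concern.** Glucose depends on recent food, so a change score is interpretable only if both values were taken under the same condition. The schedule requires a fast at some visits and leaves it open at others, and it allows the baseline itself to be either. The summaries treat all these values alike.

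Every cohort is single-arm, so no concurrent control shares the change in sampling condition. A meal-related shift could be read as a drug effect, or an unfasted baseline could hide a real rise. Laboratory data are named in the primary safety endpoint (protocol 6.1), and changes in laboratory results are a safety endpoint in SAP 5.2.2. Glucose is not an idle analyte in this trial: protocol Table 10.8-1 has a hyperglycaemia row, Table 10.7-2 records one drug-related hypoglycaemia of Grade 3 or higher on CB-839 monotherapy, and the sponsor notes in Attachment 4 that "CB-839, may affect glucose metabolism in both normal and tumor tissues".

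**Working it through.** The documents state no figure on this point, so there is nothing to reproduce. The check has four steps.

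**1. Visits set side by side.**
- Fast required: C1D1, C1D15, C2D1, C3D1 (Attachment 3).
- Chemistry drawn, fasting unspecified: Screening, C1D8, C1D22, C2D15, C3D15, Days 1 and 15 of every cycle from Cycle 4, and end of treatment (Attachment 1).
- Baseline: the required fasted C1D1 sample, or a Screening sample from the previous 3 days in an unspecified condition.

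**2. Share of draws with a required fast.** Excluding Screening and end of treatment, the number of scheduled draws through Cycle k (k ≥ 3) is 4 + 2(k − 1), of which 4 carry the requirement.
- Through Cycle 3: 4/8 = 50%.
- Through Cycle 6: 4/14 = 29%.
- Through Cycle 12: 4/26 = 15%.
- After C3D1: none.

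These are shares with fasting required, not shares of patients who actually fasted.

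**3. Artefact with zero drug effect.** Let d be the fed-minus-fasted difference, f the share of patients fed at a visit (taken as 0 at the PK visits) and b the share with an unfasted baseline. Then

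apparent mean change at the visit = d × (f − b).

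The documents give none of d, f or b. Assume d = 25 mg/dL, with 10 to 40 as the range. In the table, f is the share fed at non-PK visits.

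| b | f | Non-PK visits (C1D8, C1D22, C2D15, C3D15, C4D1 on) | PK visits (C1D15, C2D1, C3D1) |
|---|---|---|---|
| 0 | 1 | +25 | 0 |
| 0 | 0.5 | +12.5 | 0 |
| 0 | 0 | 0 | 0 |
| 0.5 | 0.5 | 0 | −12.5 |
| 1 | 1 | 0 | −25 |
| 1 | 0 | −25 | −25 |

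For d = 10 multiply by 0.4; for d = 40 multiply by 1.6. The extremes over the range are −40 (d = 40, f = 0, b = 1) and +40 (d = 40, f = 1, b = 0). In time order, the first row reads +25, 0, +25, 0, +25, 0, +25, +25 from C1D8 to C4D1: a saw-tooth, then a plateau.

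**4. Masking.** If the drug truly shifts glucose by t, the reported change is t + d(f − b). With d = 25, b = 0.5 and t = +12.5, a fasted visit (f = 0) reports 12.5 − 12.5 = 0. Even the required-fasting visits are uninterpretable when baselines are mixed.

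**The case against.** **Unspecified is not unfasted.** A reader might infer that every value outside the PK visits is post-meal, because CB-839 follows breakfast. The documents do not say so. They fix when the drug is taken, not whether the patient has eaten before the draw, and laboratory tests are to be done and reviewed before dosing, up to 48 hours ahead. This stands.

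**No built-in rise.** A reader might go further and infer that glucose must appear to climb with time on drug. It need not. Visits with and without a required fast alternate through Cycle 3, and step 3 of the check gives positive, zero and negative artefacts depending on f and b. Even the most adverse case is a saw-tooth followed by a plateau. This also stands.

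**The by-visit table partly protects itself.** Where C1D1 was fasted, the C1D15, C2D1 and C3D1 rows already give a clean contrast, so it is too strong to say that meals and drug can never be separated. That is right for those rows and patients. It does not repair mixed baselines (step 4), and it does not help the range and grade tables, which are not split.

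**The baseline problem may be only apparent.** The specific C1D1 fasting requirement could be read as overriding the general 3-day waiver. That is a fair reading, but the text does not settle it, and the number of patients affected is unknown.

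**Glucose relevance is modest.** The sponsor's note concerns FDG-PET interpretation and tumour uptake, not raised blood glucose; hyperglycaemia is absent from both monotherapy adverse event tables; and clinically significant laboratory abnormalities are captured separately as adverse events. All of this limits the consequence but does not remove the mismatch.

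**Conclusion.** The point holds. Following the plan as written compares fasted with possibly fed glucose, against a baseline that may be either, in single-arm cohorts. The resulting glucose change, out-of-range and grade summaries are confounded with meal status.

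Direction and size depend on how many patients ate before non-PK draws and before baseline. Neither is given, so the artefact cannot be derived. The mg/dL figures are illustrations that assume a common meal effect and full compliance with fasting at PK visits. Turning them into an excess of out-of-range values would need a glucose mean, an SD and a reference limit, and the documents give none of these.

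The scope is narrow: one analyte, summarised descriptively, on which no hypothesis test or sample size depends. It is a cheap improvement to safety reporting that should be made, and it does not threaten the trial's efficacy conclusions.

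**What to change.** In SAP 7.5.3, add a rule for glucose:
- Report mean change only at C1D15, C2D1 and C3D1, in patients with a fasted baseline.
- Show glucose at visits with no fasting requirement separately, as observed values. Label them as having no fasting requirement, not as unfasted.
- Split the glucose out-of-range and grade tables the same way.
- Use recorded fasting status in place of the visit label wherever it exists.

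In the protocol, reconcile Attachment 3 footnote 1 with Attachment 1 footnote 6 and Section 10.2, so that the 3-day waiver does not replace the required fasted C1D1 glucose unless the Screening sample was itself fasted. If enrolment is already complete, the SAP rule alone still helps, provided the fasting status of each baseline can be established.

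The cost is SAP wording, a little programming and a protocol clarification. No visit is added, though some patients would need glucose drawn at C1D1 instead of relying on Screening. The downside is a smaller glucose change-from-baseline table: three post-baseline visits, and only patients with a fasted baseline.

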**Pregnancy test (urine β-HCG):** Women of child-bearing potential**Urinalysis**

- Only institutional standard urinalysis is required

**ATTACHMENT 4: RECIST CRITERIA VERSION 1.1**

Source: [Eisenhauer 2009](#)

Sponsor's Note: CB-839, may affect glucose metabolism in both normal and tumor tissues. Preclinical data suggest that glucose uptake may increase with glutaminase inhibition in sensitive tissues, reflecting the pharmacodynamics effects of CB-839. False positive interpretations of progressive disease with FDG-PET scans may occur. Therefore, all FDG-PET findings suggestive of progressive disease should be confirmed by dedicated anatomic imaging (CT or MRI) for this study.

**Measurability of Tumor at Baseline****Definitions**

At baseline, tumor lesions will be categorized measurable or non-measurable as follows.

**Measurable tumor lesions**

Tumor lesions must be accurately measured in at least one dimension (longest diameter in the plane of measurement is to be recorded) with a minimum size of:

- 10 mm by CT scan (CT scan slice thickness no greater than 5 mm)
- 10 mm by caliper measurement (lesions which cannot be accurately measured with calipers should be recorded as non-measurable)
- 20 mm by chest X-ray

*Malignant lymph nodes:* To be considered pathologically enlarged and measurable, a lymph node must be  $\geq 15$  mm in short axis when assessed by CT scan (CT scan slice thickness recommended to be no greater than 5 mm). At baseline and in follow-up, only the short axis will be measured and followed. See also section below on 'Baseline documentation of target and non-target lesions' for information on lymph node measurement.

**Non-measurable tumor lesions**

Non-measurable tumor lesions encompass small lesions (longest diameter  $< 10$  mm or pathological lymph nodes with  $\geq 10$  to  $< 15$  mm short axis) as well as truly non-measurable lesions. Lesions considered truly non-measurable include: leptomeningeal disease, ascites, pleural or pericardial effusion, inflammatory breast disease, lymphangitic involvement of skin or lung, peritoneal spread, abdominal masses/abdominal organomegaly identified by physical exam that is not measurable by reproducible imaging techniques.

### **Special considerations regarding lesion measurability**

Bone lesions, cystic lesions, and lesions previously treated with local therapy require particular comment:

#### **Bone lesions:**

- Bone scan, PET scan or plain films are not considered adequate imaging techniques to measure bone lesions. However, these techniques can be used to confirm the presence or disappearance of bone lesions.
- Lytic bone lesions or mixed lytic-blastic lesions, **with identifiable soft tissue components**, that can be evaluated by cross sectional imaging techniques such as CT or MRI can be considered as measurable lesions if the soft tissue component meets the definition of measurability described above.
- Blastic bone lesions are non-measurable.

#### **Cystic lesions:**

- Lesions that meet the criteria for radiographically defined simple cysts should not be considered as malignant lesions (neither measurable nor non-measurable) since they are, by definition, simple cysts.
- ‘Cystic lesions’ thought to represent cystic metastases can be considered as measurable lesions, if they meet the definition of measurability described above. However, if non-cystic lesions are present in the same patient, these are preferred for selection as target lesions.

#### **Lesions with prior local treatment:**

- Tumor lesions situated in a previously irradiated area, or in an area subjected to other loco-regional therapy, are usually not considered measurable unless there has been demonstrated progression in the lesion. For this protocol, these tumor lesions will be considered non-measurable lesions.

